12.7 Accuracy and Precision of Laboratory Analyzer

• Performance of the Analyzer instruments to be used for this study will be tracked with 2 methods. The primary method will be the analyzer quality control QC check procedure regularly applied by the clinical site. In addition, serum controls will be

provided by Ascensia for internal research purposes only, and will not impact the study data or data collection. See Appendix C for further details.

12.8 Temperature and Humidity Logs

- The study staff will measure the temperature and humidity in the meter testing area once during the day that meter testing occurs and record the results on the appropriate log form.
- Study staff will maintain temperature log for the storage of investigational materials including the meters, test strips, meter controls, and serum controls.

13.0 Monitoring Plan

- **13.1** A monitoring plan will be completed by the Study Manager/designee prior to the study.
- **13.2** The study manager or designee will conduct a study initiation visit. The frequency of the number of monitoring visits by sponsor personnel or designee(s) will be based on the monitoring plan and will include at least 1-3 monitoring visits and a close-out visit.
- **13.3** Sponsor representatives may observe some study testing as part of study monitoring. This will be done under supervision of the Investigator.
- **13.4** Sponsor representatives will maintain participant confidentiality and will not interfere with the rights of human participants, safety, or bias study conduct.

14.0 Statistical Plan

14.1 Sample Size

- 14.1.1 The sample size requirement is based on the primary objective, section 8.0.
- 14.1.2 There will be a minimum of N = 120 study samples entered into the study. The meter results will be taken in duplicate, so that the total sample size of meter results will be 2*120 = 240.
- 14.1.3 With a sample size of n = 240 results, there is approximately a 95% chance that at least 228 of those results (95% of 240) will be "accurate" (errors within either ±12 mg/dL (±0.67 mmol/L) when the comparator result is < 100 mg/dL (5.55 mmol/L), or ±12.5% when the comparator result is \ge 100 mg/dL (5.55 mmol/L) if the evaluation (meter) system has a 96.77% chance of yielding an "accurate" result.
- 14.1.4 Conversely, there is about a 95% chance of obtaining fewer than 228 "accurate" results if the system only has an approximately 92.03% chance of yielding an accurate result.

14.1.5 Note that each glucose result obtained with the evaluation devices will be considered either 'accurate' or 'not accurate, where accuracy depends on the particular test criterion as described in section 7.0 of this protocol.

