In critically ill patients, having severe hemodynamics disturbance, decreased microcirculation, hypoxia for example, the only reliable source to assess vital parameters including blood glucose is arterial blood. Tight glycemic control and avoiding hypoglycemia as well as hyperglycemia in these severe patients is pivotal. It is noteworthy that a majority of these patients have complex comorbidities and are very often being treated by multiple agents (polypharmacy); therefore the performance of BGMS in their patients may be significantly different than when they are used for self-management of diabetes. Several studies have described variability in measurements made by different POC BGMSs or between these instruments and central laboratory analyzers, mainly due to the lower accuracy in the low blood glucose range and lower specificity of the enzymes used such as glucose oxidase, which make them susceptible to interference. That is why the more stringent accuracy assessment criteria for hospital-based blood glucose monitoring have been proposed by many international organizations, including the International Standardization Organization (ISO), and the Clinical Laboratory and Standards Institute (CLSI) and FDA.

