9.0 Clinical Study Design

- **9.1** This is an open label, prospective, single arm study. The results of the study devices will be compared to the laboratory analyzer results from the same blood sample.
- **9.2** For each BGMS, at least 120 evaluable samples and at least (N=240) evaluable results due to duplicate testing are required. Up to 150 participants may be enrolled to obtain the required number of samples.

9.3 Randomization:

- 9.3.1 Since two BGM systems will be tested in the study, the order of testing the study devices will be randomized.
- 9.3.2 Three strip lots (per BGMS) will be tested, with each sample tested with one lot. The strip lots will be randomized.
- **9.4** The results from these two BGMS systems will not be compared to each other.
- **9.5** The study design follows CLSI-POCT12-A3:2013; and ISO 20916:2019 (E) to ensure it is scientifically robust and valid.
- **9.6** Participants with non-evaluable data will be replaced as needed to obtain at least N=120 samples, and at least N=240 results (duplicate results) for each BGMS.

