12.0 Procedures

12.1 Summary

Laboratory professionals will test the blood glucose concentration of residual arterial blood samples, collected (into a tube with anticoagulant) from participants using the Contour Next and Contour Plus Elite BGMSs. For participant's safety reasons, only residual arterial blood will be used which had been collected as prescribed for clinical testing and is no longer needed for clinical purposes.

A minimum of 120 residual arterial blood samples will be tested with both BGMSs in duplicate. Approximately 2mL of whole blood will be removed from the participant's sample tube and will be used for completing a total of 4 tests using both BGMSs (two tests with Contour Next BGMS and two tests with Contour Plus Elite BGMS), a hematocrit measurement, and duplicate laboratory glucose measurements. Each participant sample will be tested using both BGMS as per the randomization schedule. After completion of the BGMS testing, each meter will be cleaned and disinfected as per the procedures in Appendix A.

The site staff will use their Laboratory Analyzer (approved by the Sponsor) for the laboratory assessment of blood glucose samples tested in duplicate (laboratory duplicate results will be averaged).

During the study, a minimum of 10 test strip vials (50 test strips in each vial) that cover a minimum of 3 test strip lots will be used for each BGMS. The test strip lots will be randomly coded as green, blue, or red to easily identify the bottles during the study. See Table 1 for the description of test strip distribution during the study (note: the 3 test strip lots are arbitrarily designated as Red, Green, or Blue).

Blood samples will be assigned to one of three test strip lots. The assignment will be made in a rotating order following the random order in which samples are received.

The order of testing for both BGMSs will also be randomized for each sample.

Meter System & Test Strips	Green Lot	Red Lot	Blue Lot	
	~40 Samples ~80 tests	· ^	~40 Samples ~80 tests	
	~40 Samples ~80 tests	^	~40 Samples ~80 tests	

 Table 1 - Strip Lot Assignments Per Meter Type

12.2 Study Staff Training

The site study staff will participate in a training session conducted by the Ascensia Study team or designee. The training will be documented and the following will be reviewed:

- 12.2.1 Protocol & case report forms
- 12.2.2 Review of the instructions for use (UG)
- 12.2.3 Review of meter control solution testing

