- 12.4.9 Strip lot (color code) will be determined via a randomization schedule provided by the Sponsor.
- 12.4.10 The testing order of the meter will also be based on a randomization schedule. Note that one Contour Next and one Contour Plus Elite BGMS per participant will be used and the meters will be disinfected after use as per procedures listed in Appendix A.
- 12.4.11 For each participant, a CONTOUR NEXT[®] BGMS, and a CONTOUR PLUS ELITE[®] BGMS will be brought to the testing area. A test strip (as assigned for the given BGMS) will be inserted into each of the 2 meters (same color code strip lot for both meters).
- 12.4.12 A drop of blood will be placed on a piece of Parafilm (or other non-absorbent material) and immediately tested with the first and second meter.
- 12.4.13 The test strips in the two meters will then be replaced, to prepare the meters for duplicate testing.
- 12.4.14 A new drop of blood will be placed on the Parafilm and immediately tested with the first and second meter for duplicate testing .
- 12.4.15 A hematocrit measurement (%) will also be performed on the sample per site hematocrit analyzer procedures.
- 12.4.16 An aliquot of blood (from the same sample as used in meter testing) will be centrifuged within 10 minutes of BG testing for separation into plasma. (See Appendix B)
- 12.4.17 The start time of centrifugation will be recorded. Centrifugation must be performed within 10 minutes of the first-meter assay.

12.4.18 The plasma will be tested in duplicate with the laboratory analyzer within 60 minutes of the meter test. If greater than 60 minutes of the meter test, plasma samples may be refrigerated or frozen. (See Appendix B)

12.5 Errors

- 12.5.1 If the meter reports an error code during blood glucose testing, the instructions shown in the UG should be followed. Re-testing is recommended (per the UG). The reason for the repeated test will be documented in the comments section of the form. No more than a total of 3 attempts are allowed.
- 12.5.2 The study staff will record all meter error codes as appropriate for the meter tests as it occurs.

12.6 Testing Schematic

Step	Test type	Description		
1	Sample prep	 Ensure collection of residual Arterial sample in collection tube containing anticoagulant (lithium/heparin). Confirm sufficient blood volume to perform all testing procedures. If so, then aliquot ~2mL into microtube and cover. 		

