14.5 Accuracy Analyses

14.5.1 Two sets of metrics will be calculated:

• Relative (Percent) Difference (RD) for reference result ≥ threshold glucose :

$$RD=\frac{M-C}{C}100\%$$

¹ Draper, N.R., Smith, H., (1998) Applied Regression Analysis, 3rd Ed., John Wiley and Sons, New York

where: M = strip/meter result and C = comparator or reference method result.

Difference (D) for reference result < threshold glucose:

$\boldsymbol{D}=\boldsymbol{M}-\boldsymbol{C}$

14.5.2 Primary objective: The threshold glucose value is 100 mg/dL(5.55 mmol/L). Accuracy will be assessed using the Clinical and Laboratory Standards Institute (CLSI) – Point-of-Care Blood Glucose Testing in Acute and Chronic Care Facilities; Draft Guideline-Third Edition (POCT12 (Draft 4) Vol.0 No.0 Replaces C30-A2 Vol.22 No.17).

i.e., D within $\pm 12 \text{ mg/dL}$ ($\pm 0.67 \text{ mmol/L}$) for comparator result < 100 mg/dL (5.55 mmol/L) and RD within $\pm 12.5\%$ for comparator result $\geq 100 \text{ mg/dL}$ (5.55 mmol/L).

For RD, the percent of results within $\pm 5\%$, $\pm 10\%$, $\pm 12.5\%$, $\pm 15\%$ and $\pm 20\%$ will be computed.

For *D*, the percent less than or equal to $\pm 5 \text{ mg/dL}$ ($\pm 0.28 \text{mmol/L}$), $\pm 10 \text{ mg/dL}$ ($\pm 0.56 \text{ mmol/L}$), $\pm 12.0 \text{ mg/dL}$ ($\pm 0.67 \text{ mmol/L}$), $\pm 15 \text{ mg/dL}$, ($\pm 0.83 \text{ mmol/L}$), and $\pm 20 \text{ mg/dL}$ ($\pm 1.11 \text{ mmol/L}$)will be computed.

The *RD* and *D* distribution tables will be constructed using a threshold of 100 mg/dL (5.55 mmol/L).

As discussed in section 14.1 (Sample Size), with n = 240, the critical number (minimum) of accurate results is 228, which yields approximately 95% chance of satisfying the criterion if the actual probability that any result will be accurate is at least 96.77%. Symbolically, this criterion is equivalent to testing the hypothesis:

*H*₀ : *Prob{accurate}*<96.77% versus the alternative:

H_1 : Prob{accurate} $\geq 96.77\%$

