This test has a power of about 95%, with n = 240, to reject H₀ if the actual probability of obtaining an accurate result is 96.77%. Conversely, there is about a 95% chance that the null will NOT be rejected if the actual probability that a result with the evaluation device would satisfy this definition of accuracy is only about 92.03%. It is possible that the sample size after the study is completed may not be exactly 240. The critical values will be approximately 95% or 98% of results (first and second parts of primary objective, respectively), and the associated hypotheses will be adjusted to reflect the change while maintaining no more than a 95% chance of rejecting the null hypotheses.

14.5.3 The second part of the primary objective states that at least 98% of the n = 240 results must fall within $\pm 15 \text{ mg/dL}(\pm 0.83 \text{ mmol/L})$ of the comparator result

(comparator < 75 mg/dL/4.16 mmol/L)) or $\pm 20\%$ of the comparator result (comparator ≥ 75 mg/dL/4.16 mmol/L). Thus, with n = 240, there must be at least 236 BGMS results satisfying this requirement. This is equivalent to testing the hypotheses:

*H*₀: *Prob{accurate}*<98.33% versus the alternative:

*H*₁: *Prob*{accurate } \geq 98.33%

There is approximately a 95% chance of rejecting H_0 in favor of H_1 if the actual probability that a meter measurement would satisfy the ±15mg/dL (±0.83 mmol/L) or 20% is 98.33%. Conversely, there is about a 95% chance that the null will NOT be rejected if the actual probability that a result with the evaluation device would satisfy this definition of accuracy is only about 96.23%.

14.6 Hematocrit Analysis – Other Objectives

- 14.6.1 Hematocrit will be measured for each participant. Mean, median, minimum, maximum, and standard deviation, will be computed for hematocrit determinations.
- 14.6.2 The effect of hematocrit on meter results will be presented via regression of differences between the meter and laboratory BG measurements against hematocrit.

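### The stated 95% pass and 5% false-pass chances treat 240 duplicate results as independent, but the design yields 120 correlated pairs per meter system

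*Combined protocol and SAP*

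**What the plan says.** Section 14.1.2 sets the sample size per system: "The meter results will be taken in duplicate, so that the total sample size of meter results will be 2*120 = 240". Sections 14.1.3 and 14.1.4 give the rule of at least 228 accurate results out of 240, with about a 95% chance of meeting it at a true accuracy of 96.77% and about a 95% chance of missing it "if the system only has an approximately 92.03% chance of yielding an accurate result".

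Section 14.5.2 repeats the claim, saying of the 228 rule: "which yields approximately 95% chance of satisfying the criterion if the actual probability that any result will be accurate is at least 96.77"%. Section 14.5.3 sets 236 of 240 for the second criterion and gives about a 95% chance of not passing when the true probability that "a result with the evaluation device would satisfy this definition of accuracy is only about 96.23"%.

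The procedures show how the 240 results arise:

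- Section 12.4.10: "one Contour Next and one Contour Plus Elite BGMS per participant will be used".
- Sections 12.4.12 to 12.4.14: the second reading uses a new strip and a new drop of the same blood sample.
- Section 9.3.2: three strip lots per system, "with each sample tested with one lot".
- Section 12.1, on the comparator: "laboratory duplicate results will be averaged".

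Sections 14.1 and 14.5 mention neither independence, nor within-sample correlation, nor a design effect.

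**The concern.** An error that belongs to the sample (an interfering drug, an extreme hematocrit), to the meter, or to the single averaged laboratory value shifts both readings of a pair in the same direction. The plan itself expects effects of this kind: section 5.0 warns that "the performance of BGMS in their patients may be significantly different than when they are used for self-management of diabetes", and section 14.6 studies hematocrit, which is measured once per participant. Zero correlation between the two accuracy outcomes of a pair is therefore not a credible default.

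Positive correlation leaves the expected percentage of accurate results unchanged but widens its spread. A good system then fails more often than stated, and an inadequate one passes more often. These figures are the plan's only numerical support for 120 samples and its only statement of how often an inadequate system would pass. The plan has no confidence bound, so a reader judging a marginal pass has nothing else to go on.

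**Working it through.** **Inputs.** 120 samples per system, two readings each (9.2, 14.1.2). Pass marks are 228 and 236 of 240 (14.5.2, 14.5.3), so at most 240 − 228 = 12 misses for criterion 1 and 240 − 236 = 4 for criterion 2. The accuracy rates are 96.77%, 92.03% and 96.23%. The within-pair correlation of the accurate/not-accurate outcomes, rho, is not in the documents and is an assumption.

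**Step 1: the plan's figures.** With X accurate results from a binomial with 240 independent trials:

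- P(X ≥ 228) at 96.77% = 95.03%
- P(X ≥ 228) at 92.03% = 5.03%, so a 94.97% chance of failing
- P(X ≥ 236) at 96.23% = 5.02%

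All three match the text, so independence of all 240 readings is what the plan assumed.

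**Step 2: 120 pairs.** With q the probability of a miss, each sample gives

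- P(2 misses) = q² + rho·q(1 − q)
- P(1 miss) = 2q(1 − q)(1 − rho)
- P(0 misses) = the remainder

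Example: true accuracy 92.03% and rho 0.5. Here q = 0.0797, q² = 0.00635 and q(1 − q) = 0.07335. So P(2) = 0.00635 + 0.5 × 0.07335 = 0.0430, P(1) = 2 × 0.07335 × 0.5 = 0.0733 and P(0) = 0.8836. Convolving this over 120 independent samples gives P(at most 12 misses) = 9.2%.

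| rho (assumed) | Criterion 1: pass at 96.77% | Criterion 1: pass at 92.03% | Criterion 2: pass at 96.23% | Effective n = 240/(1 + rho) |
|---|---|---|---|---|
| 0 | 95.0% | 5.0% | 5.0% | 240 |
| 0.2 | 93.4% | 6.7% | 6.7% | 200 |
| 0.3 | 92.7% | 7.6% | 7.6% | 185 |
| 0.5 | 91.3% | 9.2% | 9.4% | 160 |
| 0.7 | 90.0% | 10.8% | 11.1% | 141 |

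The direction is the same at every positive rho computed, from 0.1 to 1. The false-pass chance reaches 10% at rho of about 0.60 for criterion 1 and 0.57 for criterion 2. The accuracies at which criterion 1 truly has a 5% and a 95% chance of passing move from 92.0% and 96.8% (rho 0) to 91.7% and 96.9% (0.2), 91.3% and 97.1% (0.5), and 91.0% and 97.2% (0.7).

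**Step 3: which rho is plausible.** Assume unbiased normal percentage errors, a comparator of at least 100 mg/dL and the 12.5% limit. The total SD that gives 92.03% accuracy is 7.13%; for 96.77% it is 5.84%. The between-sample variance is total minus replicate variance, and rho = (P(both miss) − q²)/(q(1 − q)). Because the total SD differs, the same replicate SD implies a different rho at each accuracy.

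| Replicate SD | rho at 92.03% | False pass | rho at 96.77% | Power |
|---|---|---|---|---|
| 1.3% | 0.76 | 11.2% | 0.68 | 90.2% |
| 1.8% | 0.67 | 10.6% | 0.56 | 90.9% |
| 2.8% | 0.49 | 9.2% | 0.35 | 92.3% |
| 3.5% | 0.38 | 8.2% | 0.22 | 93.2% |
| 4.5% | 0.23 | 7.0% | 0.08 | 94.3% |

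The first two SDs bracket the repeatability CVs in the Contour Next user guide (Attachment 1) at 7.63 to 18.94 mmol/L, as far as the PDF table can be read. They come from five venous specimens on that system only, so they are a scenario and not an estimate for arterial ICU blood. The other three SDs are assumed.

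**The case against.** The strongest reply is that the effect is small and its upper end uncertain. Several parts of it stand.

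- **The pass rule is a point criterion.** Section 8.1 asks for an observed 95% or 98%, and pairing does not change that. Near the threshold correlation hardly matters: at a true accuracy of 94.9% the chance of passing is 54.8% at rho 0 and at rho 0.7. At 98% it is 99.9% and 99.0%.
- **High rho needs strongly shared error.** Each replicate has its own strip and drop. Under zero-centred normal errors, an error correlation of 0.5 gives a rho of only about 0.13 to 0.16, 0.7 gives 0.27 to 0.32, and 0.9 gives 0.55 to 0.59.
- **Bias lowers rho.** Holding accuracy at 92.03% and replicate SD at 1.8%, an assumed bias of 0, 5, 7 or 9% gives rho 0.67, 0.62, 0.48 or 0.22 and a false-pass chance of 10.6, 10.1, 9.1 or 6.9%.
- **The plan hedges.** It says approximately and about, and 93.4% at rho 0.2 could be read as within that wording. Section 9.5 also ties the design to CLSI and ISO documents.

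None of this restores the stated figures. Every scenario in the list of biases and in the tables with rho above 0 has a false-pass chance of at least 6.7%, and following a guideline's format does not supply probabilities for correlated pairs.

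**Conclusion.** The concern holds. The 95% and 5% figures in 14.1 and 14.5.2, and the 5% figure at 96.23% implied by 14.5.3, are properties of 240 independent results, which this design does not produce. For an assumed rho of 0.2 to 0.7, criterion 1 loses about 2 to 5 points of power, and the false-pass chance is about 1.3 to 2.2 times the implied 5% across the two criteria. The direction is secure; the size depends on a correlation that the documents do not give.

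The pair model covers only what is shared within a sample. Errors shared across samples, through a strip lot (about 40 samples each) or a reused meter, are not in these numbers.

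This is a correction that should be made, not a threat to the study. One neighbouring figure is a separate error: the 95% power stated for criterion 2 at 98.33% is 62.7% even with independent results.

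**What to change.** 1. Keep the pass rules (228 and 236 of 240, scaled as 14.5.2 already provides if the final number differs).
2. In 14.1 and 14.5, state that the independent unit is the sample, 120 per system. Replace the unconditional 95% and 5% figures with a table of operating characteristics at, for example, rho 0, 0.2, 0.3, 0.5 and 0.7.
3. Add a sentence saying that lot-level and meter-level errors shared across samples are not covered by that table.
4. Correct the criterion 2 power figure separately; a table over rho does not repair it.
5. Optional, since the plan has no confidence bound: if one is reported, base an exact or Wilson-type one-sided bound on an effective n of 240/(1 + rho), or conservatively on 120. A plain bootstrap degenerates with few or no misses. For 95% observed accuracy (228/240), the exact one-sided 95% lower bound is 92.0% with n = 240, 91.2% with n = 160 (rho 0.5) and 90.4% with n = 120. With no misses it is 98.8%, 98.1% and 97.5%.

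The cost is wording and one small table, with no extra samples and no change to the pass rule. The stated power and false-pass figures become slightly less favourable.

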14.2 Blood Glucose Measurements

Data analysis follows analyses and presentations described in the CLSI. *Point-of-Care Blood Glucose Testing in Acute and Chronic Care Facilities; Approved Guideline – Third Edition*. CLSI document POCT12-A3. Wayne, PA: Clinical and Laboratory Standards Institute; 2013.

14.3 Bland-Altman Plots

Modified Bland-Altman plots (the difference between each evaluation device results and reference results plotted against reference results) will be constructed.

14.4 Weighted Least Squares Regression

Weighted least squares regressions of meter results against comparator results will be performed. If M represents the meter result, and C the comparator result, the linear model can be expressed as:

$$M = \beta_0 + \beta_1 C + \varepsilon$$
$$\varepsilon \sim N(0, cv * C)$$

The parameter cv is the coefficient of variation, which is assumed to be constant across the glucose range. The weighting function will be:

$$w = C^{-2}$$

This weighting function is used to account for the constant cv nature of glucose measurement (Draper and Smith, 1998).¹

